### **1.3.4 Active phase, lead-in period**

During the 14-day lead-in period, subjects will take trigriluzole monotherapy. The 14-day period is: Week -2 and Week -1.

### **1.3.5 Active phase, combination treatment**

After Week 2, regular study visits will occur in the outpatient clinic at an interval of 14 or 21 days (depending on whether treatment includes nivolumab or pembrolizumab) as per the Study Calendar.

Subjects will receive treatment up to 109 weeks. Subjects may elect to discontinue therapy at any time for any reason. Subjects will remain on the active treatment phase of the study until confirmed disease progression, unacceptable toxicity, or withdrawal of consent, up to a maximum treatment duration of 109 weeks. Once the subject discontinues active treatment, the subject will enter the follow-up phase.

### **1.3.6 Off treatment procedures (up to 1 year)**

If a subject has discontinued active treatment due to reasons other than PD, the subject will continue to have toxicity assessments (H&P and bloodwork) and tumor assessments (CT scans, etc.) Q12 weeks (window can be widened to  $\pm$  28 days) for up to 1 year from the start of treatment.

Subjects should be strongly encouraged to adhere to in-person toxicity assessments and tumor assessments per protocol for the 1-year active phase of the protocol. However, subjects who are unable or unwilling adhere to in-person assessments (but do not withdraw consent to be followed) should be contacted Q12 weeks to assess for adverse events. Safety labs and tumor assessments should be obtained at outside facilities if possible. This practice is allowable because it is preferable over removal of the patient from study entirely, and it will not be considered to be a protocol deviation.

If cancer return/progression is observed within the 1-year treatment period (in the opinion of the treating investigator, no strict criteria) and the risk/benefit ratio of restarting study therapy (combination therapy or trigriluzole monotherapy) is acceptable to the treating investigator, the patient may be restarted on therapy with the approval of the PI for up to 12 additional months.

### **1.3.7 Long term Follow-up phase**

Subjects will remain in the follow-up phase of the trial for up to 3 years until start of another therapy, withdrawal of consent, or death. Subjects or their caretakers will be contacted by a member of the study team every 12 weeks ( $\pm$  28 days) to collect post-study survival status (alive or deceased) and receipt of subsequent anticancer therapy (yes or no). If available, start date and type of subsequent anticancer therapy should be documented in the medical record or research shadow chart. Any method of data collection is acceptable for long-term follow-up (medical records, phone, electronic means, social security death index website, etc.) The source of the information should be noted in the medical record or research shadow chart.

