**RUTGERS | eIRB**  
**APPROVED**

IRB ID: Pro20170000453  
Approval Date: 10/4/2019  
Expiration Date: 4/3/2020

- survival time (OS), landmark survival rates at 1 and 2 years
- duration of response for responding patients
- time to progressive disease (PFS)
- time to treatment failure
- time to next therapy or death (TTNTD)
- freedom from new metastases

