 **RUTGERS | eIRB**  
APPROVED  
Form Version v120116

IRB ID: Pro20170000453  
Approval Date: 10/4/2019  
Expiration Date: 4/3/2020

	Off treatment but on study Q6 weeks	Off treatment but on study Q12 weeks	Safety Follow-up (12 weeks after last dose of rx)	Long-Term Follow-up Q12 weeks
Scheduling Window (Days):	±14	±14	±28	± 28
Prior and Concomitant Medication Review	X	X	X	
Assess Baseline Symptoms/Adverse Events and Compliance	X	X	X	
Vital Signs and Weight, ECOG Performance Status, Physical Examination	X	X	X	
Routine Safety Laboratory Studies	X	X	X	
Tumor Assessment 		X	X	
Post-study survival status, and receipt of subsequent anticancer therapy				X

Footnotes

1. If a subject has discontinued active treatment due to reasons other than PD (such as toxicity or patient preference), the subject will continue to have CT scans and follow-up visits to monitor them until Week 49.
2. Tumor Assessment must be performed at the same Weeks as subjects who remain on active treatment (Week 7, Week 13, and then Q12 weeks up until Week 49).
3. Safety follow-up visit will occur at Week 61 for subjects who complete all treatment (Week 49), but it will occur prior to Week 61 if active treatment is discontinued early for PD or other reasons.
4. Long-term Follow-up. Subjects will remain in the follow up phase of the trial for up to 3 years until the start of another therapy, withdrawal of consent or death.

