#### **Secondary Hypotheses and Endpoints**

We hypothesize that combination therapy will lead to regression of tumors. Therefore, the following secondary endpoints will be recorded:

- objective response rate (ORR) according to modified RECIST v.1.1.
- survival time (OS)
- landmark survival rates at 1 and 2 years
- duration of response for responding patients
- time to progressive disease (PFS)

- time to treatment failure
- time to next therapy or death (TTNTD)
- freedom from new metastases

We hypothesize that features in the tumor microenvironment (TME) and/or tumor genome may be associated with response to therapy. Therefore, we will quantify changes in immune cell phenotypes and gene expression, markers of angiogenesis, metabolic effector molecules, and exosomal formation and contents.

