### **Analysis Plan for Secondary Endpoints**

Clinical Secondary Endpoints. The frequency of AEs and SAEs will be recorded. Clinical measures of efficacy will be described, including overall survival, progression-free survival, etc. (see Secondary Endpoints above). Descriptive statistical will be used, except where otherwise specified. Continuous variables will be presented by summary statistics (such as mean, median, standard error and 90% CI) and the categorical variables by frequency distributions (i.e., frequency counts, percentages and 90% CI).

Correlatives. We will collect pre- and post-treatment tumor samples from responders and non-responders to test for differences in signal transduction in key pathways (MAPK, Pi3K/AKT), presence of TILs and other immune effector cells, PD-L1 expression, the expression of VEGF, IL-8, CD34, CCL2, M-CSF, and immune-related gene expression profile. We will determine if the presence of GRM1 expression, activating mutations in B-RAF or N-RAS, or PTEN inactivation (or activating B-RAF mutations and PTEN inactivation together) in the pre-treatment tumor samples correlates with response to therapy. We will examine the change in key pathways before and after the trigriluzole monotherapy lead-in period (Baseline vs. Week 1) and compare to the samples taken after exposure to combination therapy (Week 7).

We will also collect pre- and post-treatment peripheral blood samples from responders and non-responders and determine the expression of VEGF, IL-8, CD34, CCL2, and M-CSF, and changes in the quantity and contents of tumor-derived exosomes. We will determine if the expression of these markers in pre-treatment peripheral blood samples correlates with response to therapy. Next, we will compare the pre-treatment and post-treatment blood and tumor samples to see if response to treatment correlates with activation or suppression of signal transduction through the MAPK and PI3K/AKT pathways, changes in immune effector cells in the tumors and peripheral blood, or changes in the quantity or contents of peripheral blood exosomes.

Treatment effect for each patient will be measured as paired differences between pre- and post- measurements of these parameters at various times. Transformation of the data will be performed if appropriate, e.g. log transformation, and hence treatment effect will be expressed on a log scale.

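### Survival follow-up stops at the start of another therapy and no censoring rule is given for overall survival, so the 2-year survival rate is open to informative censoring of unknown size and sign

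*Combined protocol and SAP*

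**What the plan says.** - **Endpoints.** Section 1.1.3 lists "survival time (OS), landmark survival rates at 1 and 2 years" among the secondary endpoints, and Section 6.1 repeats "landmark survival rates at 1 and 2 years".
- **Where survival is collected.** In the follow-up calendar (Section 1.10), the row "Post-study survival status, and receipt of subsequent anticancer therapy" is marked only in the Long-Term Follow-up column.
- **When that phase ends.** Section 1.3.7 says "for up to 3 years until start of another therapy, withdrawal of consent, or death". Footnote 4 of the calendar has the same rule: "for up to 3 years until the start of another therapy, withdrawal of consent or death".
- **How data may be obtained.** Section 1.3.7 accepts any source, including records, telephone and a death index, but says so about this same phase.
- **Analysis.** Section 6.1, Analysis Plan for Secondary Endpoints, says "Clinical measures of efficacy will be described, including overall survival, progression-free survival, etc". It adds percentages with 90% intervals for categorical variables. It gives no estimator, time origin or censoring rule for survival. The missing-data paragraph deals only with replacing subjects for DLT evaluation.
- **Other observation.** Under Section 1.3.5, "Subjects will remain on the active treatment phase of the study until confirmed disease progression, unacceptable toxicity, or withdrawal of consent", up to 109 weeks. Those who stop for reasons other than progression have visits up to 1 year (Section 1.3.6), and a safety visit follows 12 weeks after the last dose. Section 6.1 (Compliance/Adherence) ends follow-up of subjects who leave for non-compliance.

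**The concern.** Stopping at the next therapy suits time to next therapy or death, which needs only the first of those two events. It does not suit overall survival, which needs the deaths that come afterwards.

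Subjects who start another therapy have mostly progressed, so leaving observation at that point is related to prognosis. The direction is not obvious. If most progressors go on to another therapy and then die, those deaths are missed and survival looks too good. If many progressors are too ill for further therapy and die under observation while fitter ones leave, survival looks too poor.

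The existing visits protect most of the 1-year rate. They do not protect the 2-year rate for a subject who progresses and starts another therapy. At stake is a reported 2-year rate that omits a substantial share of deaths and rests on very few subjects.

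**Working it through.** **No survival figure to reproduce.** The documents state no survival rate, event count or precision. The sample size adds up: 9 + 3 = 12 and 21 + 6 = 27.

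**Main model (all rates are assumptions).** Times are exponential, with 400,000 subjects per scenario.
- Median time to progression 4, 6 or 9 months; no death before progression; everyone observed until progression.
- 20, 40 or 60% of progressors too ill for further therapy, with median survival after progression of 3 months. They are observed until death.
- The others have median survival after progression of 9, 12 or 18 months, and start next therapy a median of 1.5 months after progression.
- For those who start next therapy, observation ends at the later of that start and the 12-week safety visit.
- Error = Kaplan-Meier on the observed times minus true survival.

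This gives 3 × 3 × 3 = 27 scenarios, with true 24-month survival of 14-56%.

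**Middle scenario (6 months, 40%, 12 months).** With progression rate *a* and post-progression death rate *d*, true survival in each group is exp(-at) + a[exp(-dt) - exp(-at)]/(a - d). At t = 24 months, exp(-at) = 2^-4 = 0.0625.
- Too ill: exp(-dt) = 2^-8 = 0.0039 and a/(a - d) = (1/6)/(1/6 - 1/3) = -1, so survival = 0.0625 + 0.0586 = 0.121.
- Others: exp(-dt) = 2^-2 = 0.25 and a/(a - d) = (1/6)/(1/6 - 1/12) = 2, so survival = 0.0625 + 0.375 = 0.4375.
- Overall: 0.4 × 0.121 + 0.6 × 0.4375 = 0.311.

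Simulated Kaplan-Meier gives 0.313, an error of +0.2 points, because the two losses offset each other. Even so, 35% of deaths by 24 months are unobserved. The share under observation at 24 months is 0.103: 12 × 0.103 = 1.2 and 27 × 0.103 = 2.8, against 12 × 0.311 = 3.7 and 27 × 0.311 = 8.4 alive. With 12 subjects, the chance that nobody is under observation is (1 - 0.103)^12 = 27%; the chance that nobody is alive is (1 - 0.311)^12 = 1%.

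**Ranges.** Section 1.7.12 asks for progression to be confirmed, by repeat assessment 4-12 weeks later or by clinical deterioration. The lag rows delay the last dose, safety visit and next therapy accordingly.

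| Scenarios | Error at 24 months (points) | Error at 12 months (points) | Deaths by 24 months unobserved |
|---|---|---|---|
| 27, no lag | -13 to +15 | -5 to +6 | 18-53% |
| 27, 4-week lag | -12 to +12 | -4 to +4 | 16-48% |
| 27, 8-week lag | -11 to +10 | -3 to +3 | 15-44% |
| 27, 12-week lag | -10 to +9 | -2.5 to +2.3 | 13-40% |
| 9, nobody too ill, no lag | +18 to +26 | +6 to +11 | 67-76% |
| 9, nobody too ill, 8-week lag | +11 to +17 | +3 to +5 | 52-65% |

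With no lag, the median absolute error in the 27 scenarios is 5 points at 24 months and 2 at 12 months. At 24 months the error is downward by more than 1 point in 11 scenarios and upward by more than 1 point in 12. The expected number under observation at 24 months is 0.4-2.7 of 12 and 0.8-6.0 of 27, against 1.7-6.7 and 3.8-15.0 alive. These counts need no estimator.

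**Second model.** Constant hazards are set so that true 1-year survival is 62% or 73% (the nivolumab melanoma figures in Section 1.4.7, used only to set a range). It assumes 20, 40 or 60% start another therapy by 2 years, and a death hazard after versus before next therapy of 0.5 to 4. The safety visit is not credited. Kaplan-Meier censored at next therapy tends to exp(-2d0), with d0 the yearly death hazard before next therapy. The 2-year error runs from -13 to +25 points and the 1-year error from -7 to +13. For 62%, 40% and ratio 3, true 2-year survival is 34.0% and the estimate 47.5%, an error of +13.5. In the same case, counting censored subjects as alive gives about +28, and dropping them about +2.

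**Sampling error for scale.** The 90% half-width at a rate of 50% is 1.645 × sqrt(0.25/27) = 16 points with 27 subjects and 1.645 × sqrt(0.25/12) = 24 points with 12.

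**The case against.** The strongest reply is that little depends on this. Survival is secondary, descriptive and without a comparator. It pools several tumour types, treatment histories and dose cohorts, and no stated decision uses the 2-year rate. In the middle scenario the net error is close to zero, and every error in the 27 scenarios is below the 16-point sampling half-width for 27 subjects. All of this stands and sets the priority. It does not answer the missed deaths or the small number under observation, and more subjects would not remove a systematic error.

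Second, the text may be meant more generously. Section 1.3.7 also asks for the start date and type of later therapy and allows a death index, so a site might keep recording deaths. That is possible, but nothing requires it and the stop is written twice. If continued follow-up was intended, a clarifying sentence in both places settles it.

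Third, Kaplan-Meier is the review's assumption. Section 6.1 offers percentages with 90% intervals, which could be applied to a landmark rate. This is fair: the error figures are not a property of the plan. But a percentage also needs a rule for subjects of unknown status, and the +2 and +28 results above show how much that choice matters.

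Finally, the 1-year statement depends on the model: up to +11 points if no progressor is too ill, and -7 to +13 in the second model. Section 1.3.2 expects the study to take 2 years, which could itself cut off 2-year status. Both points are correct.

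**Conclusion.** The concern holds. The only phase in which survival status is scheduled ends at the next therapy, and the plan does not say how the resulting unknown status is handled.

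The 2-year rate is the one exposed. In the 27 main scenarios its error is -13 to +15 points with no confirmation lag and -10 to +9 with a 12-week lag, and the sign cannot be settled from the documents. Large upward errors of +18 to +26 points arise only if no progressor is too ill for further therapy. The 1-year error in the main scenarios is a few points.

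The error figures rest on assumed event rates and on Kaplan-Meier censored when follow-up ends. The loss from non-compliance is not modelled. The primary endpoint and time to next therapy or death are unaffected. This should be corrected, at low-to-moderate priority.

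**What to change.** 1. In Section 1.3.7 and footnote 4 of the follow-up calendar, remove the start of another therapy as an end of survival follow-up. Collect vital status every 12 weeks until death, withdrawal of consent or 3 years, and keep recording the date of next therapy for time to next therapy or death.
2. In Section 6.1 (Compliance/Adherence), limit the no-follow-up sentence to study visits, so that vital status is still collected.
3. In Section 6.1 (Analysis Plan for Secondary Endpoints), state that overall survival and the landmark rates are estimated by Kaplan-Meier from the first day of treatment (Day -14), censored at the last date known alive, with numbers at risk at 1 and 2 years.
4. Reconcile the 2-year study length in Section 1.3.2 with the 2-year landmark and the 3-year follow-up.

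This removes the loss of deaths after next therapy, whichever way the error runs. The cost is a few more status checks for some of the 12-27 subjects, by methods Section 1.3.7 already permits. Deaths that are not collected during the study may be hard to recover later.

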### **1.3.8 Study Population**

#### **Inclusion of Women and Minorities**

Both men and women and members of all ethnic groups are eligible for this trial. No special recruitment will be performed based on gender or minority status.

#### **Contraception for Men and Women of child-bearing potential (WOCBP)**

Women of child-bearing potential (WOCBP) are defined as women who have the potential to become pregnant. Peri-menopausal women are considered WOCBP and must use effective contraception. Women who are menopausal (defined as no menses in  $>1$  year) are excluded. WOCBP must have a negative serum pregnancy test prior to the first dose. During study treatment, pregnancy testing may be performed as indicated at the treating physician's discretion. WOCBP may opt out of pregnancy testing if they provide an acceptable reason with their treating provider (such as 100% abstinence from heterosexual intercourse).

WOCBP and men must agree to use effective contraception during the study participation, and for 5 months after the last dose of the drug. Effective contraception options include: 100% abstinence from heterosexual intercourse, surgical (tubal sterilization or partner's vasectomy), intrauterine device, and combination hormonal contraceptives including birth control pills, skin patches, shots, under-the-skin implants, or vaginal rings. Barrier methods of birth control such as condoms are not adequate as primary method of contraception, but may be used as a secondary method.

Should a woman become pregnant or suspect she is pregnant while she or her partner is participating in this study, she should inform her treating physician immediately.

Protocol Number: RCINJ# 051707

PI Name: [name]

Protocol Title: A Phase I Study to Evaluate  
the Safety of Trigriluzole (FC-4157/BHV-  
4157) in Combination with PD-1 Blocking  
Antibodies

8

RESERVED FOR IRB STAMP  
DO NOT MODIFY THIS SPACE

Form Version v120116

IRB ID: Pro20170000453  
Approval Date: 10/4/2019  
Expiration Date: 4/3/2020

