#### **1.4.5 Potential Risk to Fetal Development.**

Trigriluzole has not yet been assessed in fertility and fetal development studies. Riluzole has been assessed previously and has been characterized as a Category C drug. As described in the USPI, oral administration of riluzole to pregnant animals during the period of organogenesis caused embryotoxicity in rats and rabbits at doses of 27 mg/kg and 60 mg/kg, respectively, or 2.6 and 11.5 times, respectively, the recommended maximum human daily dose on a mg/m^2 basis. Evidence of maternal toxicity was also observed at these doses. When administered to rats prior to and during mating (males and females) and throughout gestation and lactation (females), riluzole produced adverse effects on pregnancy (decreased implantations, increased intrauterine death) and offspring viability and growth at an oral dose of 15 mg/kg or 1.5 times the maximum daily dose on a mg/m^2 basis. There are no adequate and well-controlled studies in pregnant women. Riluzole should be used during pregnancy only if the potential benefit justifies the potential risk to the fetus.

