- 6) Patients with active, untreated central nervous system (CNS) metastases will be excluded from this clinical trial because of their poor prognosis and because they often develop progressive neurologic dysfunction that would confound the evaluation of neurologic and other adverse events. Patients who have brain metastases that been treated with radiation therapy or surgery will be required to have a washout period of at least 3 weeks prior to study entry, must be neurologically asymptomatic, and must not require systemic steroids.
- 7) Women of child-bearing potential and men must agree to use adequate contraception prior to the start of treatment, for the duration of treatment, and for 5 months after last dose of study treatment.
- 8) Patients with immune deficiency have impaired immune responses, therefore, known HIV-positive patients are excluded from the study because of interference with the correlative goals of the study.
- 9) Patients who require one or more of the following prohibited medications: fluvoxamine, cimetidine, amiodarone, efavirenz, fluoroquinolones, fluvoxamine, furafylline, interferon, methoxsalen, mibefradil, or ticlopidine.

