### **Procedures for Risks to Embryo, Fetus, and/or Pregnant Subjects**

Trigriluzole has not yet been assessed in fertility and fetal development studies. Riluzole has been assessed previously and has been characterized as a Category C drug. As described in the USPI, oral administration of riluzole to pregnant animals during the period of organogenesis caused embryotoxicity in rats and rabbits at doses of 27 mg/kg and 60 mg/kg, respectively, or 2.6 and 11.5 times, respectively, the recommended maximum human daily dose on a mg/m^2 basis. Evidence of maternal toxicity was also observed at these doses. When administered to rats prior to and during mating (males and females) and throughout gestation and lactation (females), riluzole produced adverse effects on pregnancy (decreased implantations, increased intrauterine death) and offspring viability and growth at an oral dose of 15 mg/kg or 1.5 times the maximum daily dose on a mg/m^2 basis. There are no adequate and well-controlled studies in pregnant women. Riluzole should be used during pregnancy only if the potential benefit justifies the potential risk to the fetus.

Women of child-bearing potential (WOCBP) are defined as women who have the potential to become pregnant. Peri-menopausal women are considered WOCBP and must use effective contraception. Women who are menopausal (defined as no menses in >1 year) are excluded. WOCBP must have a negative serum pregnancy test prior to the first dose. During study treatment, pregnancy testing may be performed as indicated at the treating physician's discretion. WOCBP may opt out

of pregnancy testing if they provide an acceptable reason with their treating provider (such as 100% abstinence from heterosexual intercourse).

WOCBP and men must agree to use effective contraception during the study participation, and for 5 months after the last dose of the drug. Effective contraception options include: 100% abstinence from heterosexual intercourse, surgical (tubal sterilization or partner's vasectomy), intrauterine device, and combination hormonal contraceptives including birth control pills, skin patches, shots, under-the-skin implants, or vaginal rings. Barrier methods of birth control such as condoms are not adequate as primary method of contraception, but may be used as a secondary method.

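### The opt-out from pregnancy testing is not limited to on-treatment tests, so it conflicts with the mandatory negative serum test before the first dose

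*Combined protocol and SAP*

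**What the plan says.** Section 1.3.8 (Study Population), in its part on contraception, gives three statements in this order:

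1. "WOCBP must have a negative serum pregnancy test prior to the first dose".
2. "During study treatment, pregnancy testing may be performed as indicated at the treating physician" sees fit; no on-treatment test is compulsory.
3. "WOCBP may opt out of pregnancy testing if they provide an acceptable reason with their treating provider (such as 100% abstinence from heterosexual intercourse".

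Section 4.1.8, under Procedures for Risks to Embryo, Fetus, and/or Pregnant Subjects, carries the same three statements in the same order. There too a woman may opt out "of pregnancy testing if they provide an acceptable reason with their treating provider".

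Footnote 2 of each study calendar in section 1.10 (nivolumab and pembrolizumab) repeats the first two statements, specifying beta-HCG. It does not mention an opt-out.

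The only reproductive item among the numbered eligibility criteria in section 4.1.1 is exclusion 7: "Women of child-bearing potential and men must agree to use adequate contraception prior to the start of treatment", through treatment and for 5 months after it. Section 1.3.8 counts abstinence as contraception: "Effective contraception options include: 100% abstinence from heterosexual intercourse".

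On fetal risk, section 1.4.5 says: "Trigriluzole has not yet been assessed in fertility and fetal development studies". It also reports that riluzole, the active metabolite, was embryotoxic in rats and rabbits and that in rats "riluzole produced adverse effects on pregnancy (decreased implantations, increased intrauterine death" among other effects.

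**The concern.** The first two statements each say when they apply. The third does not: it speaks of pregnancy testing in general. Taken at its widest, it reaches the pre-dose test, and an unqualified exception then stands in the same paragraph as a mandatory safety rule.

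The example offered as an acceptable reason adds to the difficulty. Abstinence is a sound reason to expect no new pregnancy during treatment, but a statement of abstinence does not rule out a pregnancy that already exists, which is what the pre-dose test is for. Section 1.4.5 allows riluzole in pregnancy only where the likely benefit justifies the fetal risk. Nobody can make that judgment when pregnancy status is unknown.

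At stake is the possible exposure of an unrecognised pregnancy to a drug with no fetal development data of its own and an embryotoxic active metabolite.

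**Working it through.** No sample size, error rate or other figure is involved, so the check is a comparison of every place where the documents deal with pregnancy testing.

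| Place | Test before first dose | Tests during treatment | Opt-out |
|---|---|---|---|
| Section 1.3.8 | Mandatory | Physician's discretion | Yes, no timing stated |
| Section 4.1.8 | Mandatory | Physician's discretion | Yes, no timing stated |
| Section 1.10, nivolumab calendar, footnote 2 | Mandatory | Physician's discretion | Not mentioned |
| Section 1.10, pembrolizumab calendar, footnote 2 | Mandatory | Physician's discretion | Not mentioned |
| Section 4.1.1, inclusion 1 to 10 | Not mentioned | Not mentioned | Not mentioned |
| Section 4.1.1, exclusion 1 to 9 | Not mentioned | Not mentioned | Not mentioned |

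So the pre-dose test is required in 4 places, the opt-out appears in 2 of those 4, and pregnancy is named in 0 of 10 inclusion and 0 of 9 exclusion criteria.

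**Reading A: the opt-out covers on-treatment tests only.** Three things support it. The sentence directly follows the on-treatment one. It has a job there, because discretion belongs to the physician while the opt-out belongs to the patient, who may decline a test the physician wants. And it agrees with both calendar footnotes.

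**Reading B: the opt-out covers all pregnancy tests.** What supports it is the wording: there are no timing words, although both neighbouring sentences have them. Under this reading the paragraph contradicts itself. A woman who has not been tested does not have a negative result, so she fails the mandatory rule, yet a provider who accepts her reason has acted within the opt-out. The documents do not say which sentence prevails.

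**Does anything else settle it?**

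- The calendar footnotes support Reading A but are silent on the opt-out. They neither limit nor override it. Neither calendar has a separate row for the pregnancy test; the requirement sits inside the footnote to the routine safety laboratory row.
- Exclusion 7 does not settle it. A declaration of abstinence meets the contraception condition and is also the protocol's own example of a reason to opt out, so one statement serves both purposes.
- Registration (section 1.3.8, Study Enrollment Procedures) depends on a signed eligibility checklist. The checklist is not reproduced. If it follows the numbered criteria, which is an assumption, nothing on it would prompt a look for a pregnancy test.

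Reading A is the better one, but the text does not state it and nothing elsewhere expressly excludes Reading B.

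**The case against.** The strongest reply is that the protocol already answers the question. The pre-dose test is mandatory wherever it appears, and a specific mandatory rule should prevail over a general permissive sentence. The calendars, which staff follow visit by visit, repeat the rule without the opt-out. On this view the sentence is loosely drafted and the design contains no error.

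Most of that stands. It establishes that Reading A is probably what was meant and that staff working from the calendar would do the test. It does not establish that the wording is safe to leave, because sections 1.3.8 and 4.1.8 are where a provider would look for the rule on exceptions, and there the exception is unqualified.

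Two stronger readings are tempting, and the documents do not support them:

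- A reader might infer that the protocol waives the pre-dose test for women who report abstinence. It does not say so. The mandatory sentence stands in the same paragraph, and the opt-out also needs a reason the provider accepts.
- A reader might infer, from the absence of pregnancy among the exclusion criteria, that a pregnant woman could be dosed. A woman with a positive test is already barred by the requirement for a negative one. The gap concerns only a woman who is not tested.

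**Conclusion.** The point holds as a low-probability safety ambiguity. In sections 1.3.8 and 4.1.8 the opt-out is not confined to on-treatment tests, and so it conflicts with the only mandatory pregnancy test in the protocol.

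Its size cannot be put as a rate. The documents do not say how many of the 12 to 27 subjects will be WOCBP, and harm would need several things together: the wider reading, a provider who accepts a reason, and an undetected pregnancy. The case for acting rests on how serious the consequence would be and how little the correction costs.

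A reader might also want to compare the cohort doses with the animal dose multiples in section 1.4.5. That comparison has no bearing on what the opt-out covers, and the documents do not state the maximum human dose on which those multiples are based. The fetal-risk statements in section 1.4.5 suffice without it.

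**What to change.** In both sections 1.3.8 and 4.1.8, begin the opt-out sentence with *During study treatment,* and add after it: *The serum test before the first dose cannot be waived.* If the sponsor means the opt-out to cover the pre-dose test, that should be stated and justified, and footnote 2 of both calendars brought into line.

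The cost is one phrase and one sentence in each of two places. For a WOCBP who reports abstinence, the burden is one blood test that both calendars already require.

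Two further changes are optional, and the point does not depend on them:

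- Add pregnancy to the exclusion criteria. This restates an existing bar on dosing and would not by itself resolve the opt-out wording, but it would put the check among the numbered criteria.
- State whether the 14-day rule for routine laboratory tests in footnote 2 also applies to the pregnancy test. Because the test is described in the same footnote, that reading is plausible. If the rule does not apply, section 1.3.3 allows up to 28 days from screening to registration and 14 more to the start of treatment, so a screening test could be 28 + 14 = 42 days old at the first dose. Applying the 14-day rule would mean a repeat test at Week -2 for some WOCBP.
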